#### **ABBREVIATIONS**

AbbreviationDefinitionAEAdverse events

ATC Anatomic Therapeutic Chemical BLQ Below Limit of Quantification

BMI Body mass index BP Blood pressure

CDC Centers for Disease Control

CI Confidence interval
CKD Chronic kidney disease
CRF Case report form
CSR Clinical study report

DSMB Data and Safety Monitoring Board

ECG Electrocardiogram

eCRF Electronic Case report form

eGFR Estimated glomerular filtration rate

ESRD End-stage renal disease

FAS Full analysis set

HP Hyperphosphataemia

ICH International Conference on Harmonisation

iPTH Intact parathyroid hormone

IxRS Interactive Voice/Web Response System

LOQ Limit of Quantification

MedDRA Medical Dictionary for Regulatory Activities

N/A Not Applicable
PB Phosphate binder
PPS Per-protocol set
PT Preferred term

SAE Serious adverse event
SAP Statistical analysis plan
SAS® Statistical Analysis System
SMQ Standardised MedDRA Query

SOC System Organ Class

TEAE Treatment-emergent adverse event

TSAT Transferrin saturation

UIBC Unsaturated iron binding capacity

WHO World Health Organisation

# **DOCUMENT HISTORY**

Version	Date	Modification
Final v1.0	27-DEC-2018	N/A
	_	N/A  - Typo corrected in abbreviations section on ATC. N/A added Tables 4, 5 and 6: Last category extended to include 18 years. Indeed, we may have subjects enrolled at less than 18, but aged of 18 years during the study. Footnote added Section 3.2: missing compliance added on the first programmable protocol violation Section 4.2.6: Last category for the age at randomisation extended to include 18 years. Indeed, we may have subjects enrolled at less than 18, but aged of 18 years at the time of randomisation Sections 4.2.8.1 and 4.2.8.2: Precisions added on the derived analysis visits (applying windowing as defined in section 4.2.9) to be used Section 4.2.8.4: Imputation rule added if value > X for laboratory parameters Section 4.2.9: Column "Analysis visit" added to be consistent with the reference in sections 4.2.8.1 and 4.2.8.2. Precisions added on the CRF visits to be used to derive "End of stage 1" and "End of stage 2" for safety analysis, and the fact that the last non missing assessment collected in each period will be reported under "End of Stage 1" and "End of Stage 2" Section 4.6: Details added on the compliance calculation for Stage 1 and Stage 2 Section 4.7: details added regarding conversion factor to convert mmol/L into mg/dL for serum phosphorus Section 4.9.1: Slashes removed from System/Organ/Class in order to be system organ class. Addition of AE table by SOC and PT, and by age Section 4.9.2: details added for the derivation of an episode of sustained hypercalcaemia Section 4.9.3: Formula added to derive Transferrin Saturation (%) laboratory parameter. Unsaturated Iron Binding Capacity parameter added in Table 10 Section 7.1: Numbering updated in AE section due to duplicate numbering. Addition of 2 tables related to Serum total corrected calcium (Table 14.4.3.1 and 14.4.4.1), numbering updated on the Calcium-Phosphorus product tables. Addition of 2 tables related to TEAE by SOC and PT, and by Age (Table 14.3.1.30 and 14.3.1.31) Section 7.2: Addition of list
Final v3.0	20-MAR-2019	more than one batch was used. Numbering updated on Listing 16.1.6.2 to become Listing 16.1.6.3.  - Addition of updates detailed in the SAP Addendum dated of 22
1 11141 VJ.U	20-111/AIX-2017	February 2019:

- Section 4.2.8.5: imputation of missing or partial dates on disease history
- Section 4.6: addition of new exposure to study drug tables by age group
- Section 4.9.1: (a) addition of a new listing of AEs occurring in patients randomized but not treated; (b) in the tables by SOC and PT and by time of onset, the denominator is the number of patients at risk at the beginning of the period (excluding those who have withdrawn or completed).
- Section 4.9.3:
  - (a) TSAT will not be derived and presented;
  - (b) In Table 11, last age category for the eGFR formula extended to include 18 years. Indeed, we may have subjects enrolled at less than 18, but aged of 18 years during the time of the study;
  - (c) For the shift tables, a list of parameters has been added for which we will not produce shift tables due to normal ranges not available.
- Sections 7.1 and 7.2: new tables and listing added per the above updates.
- Section 4.4: addition of the early termination and reasons table by age group.
- Section 4.6:
- (a) Addition of exposure to PA21 drug tables during Stage 1, Stage 2 and overall by gender, by region and by formulation (tablets only, sachets only, both);
- (b) Addition of details regarding exposure variables for patients with all dispensed tablets/sachets or bottles unused, reported as lost and no tablets/sachets or bottles returned dates.
- Section 4.7.1: addition of change from baseline sP in PA21 Group end of stage 1 table (FAS population) by formulation, by serum phosphorus at baseline according to the age related normal range (Above vs. within + below), and by age group\*serum phosphorus at baseline according to the age related normal range (first age group will be excluded as no subject in).
- Section 4.9.1:

9

- (a) In the tables by SOC and PT and by age group, the denominator is the number of patients in each age group.
- (b) Removal of the additional listing of AEs occurring in patients randomized but not treated
- -Sections 7.1 and 7.2: new tables added or listing removed per the above updates.

#### 1. INTRODUCTION AND OBJECTIVES OF ANALYSIS

#### 1.1. Introduction

Hyperphosphataemia (HP) is a common and serious complication in subjects with chronic kidney disease (CKD), particularly those with end-stage renal disease (ESRD) requiring dialysis. In the paediatric population, CKD is most commonly caused by congenital anomalies of the kidney and urinary tract such as aplasia/hypoplasia/dysplasia and obstructive uropathy. The frequency of such conditions is low. Glomerular diseases of various aetiologies, (e.g., polycystic kidneys, pyelonephritis) can also cause CKD, but with a lower frequency. HP plays an important role in the pathophysiology of major CKD complications for example secondary hyperparathyroidism, renal bone disease and cardiovascular disease, and appears to promote the progression of CKD towards ESRD. High levels of serum phosphorus are considered to be a risk factor for mortality, morbidity and hospitalisation in patients with ESRD.

Complications most relevant to the paediatric population are renal bone disease, also called renal osteodystrophy (sometimes referred to as mineral bone disease), cardiovascular disease and growth failure.

As the efficacy and safety of PA21 has been confirmed in adult subjects with CKD on dialysis, the aim of this Phase 3 clinical study is to demonstrate similar efficacy of PA21 in paediatric and adolescent subjects with CKD, and to provide safety and dosing information for this subject population. The Phoslyra group provides information for a descriptive comparison of PA21 against a commonly used calcium-based phosphate binder (calcium acetate).

This Statistical Analysis Plan (SAP) has been developed for the final analyses of protocol PA-CL-PED-01 (Version 2.0, 22 September 2015), prior to final database lock. It outlines the efficacy and safety analyses, including tables, listings, and graphical presentations to be included in the Clinical Study Report (CSR). A complete draft SAP has been developed and approved by the sponsor statistician before any significant accumulation of data.

# 1.2. Objectives of Statistical Analysis

The primary objective of this study is:

• To evaluate the efficacy of PA21 in reducing serum phosphorus levels in paediatric and adolescent subjects with CKD at the end of Stage 1.

The secondary objectives of this study are:

- To evaluate the efficacy of PA21 in maintaining the serum phosphorus lowering effects in paediatric and adolescent subjects with CKD at the end of Stage 2.
- To evaluate the safety of PA21 in paediatric and adolescent subjects with CKD.
- To evaluate the efficacy of Phoslyra in reducing and maintaining serum phosphorus levels in paediatric and adolescent subjects with CKD at the end of Stages 1 and 2.
- To evaluate the safety of Phoslyra in paediatric and adolescent subjects with CKD.

This SAP is designed to outline the methods to be used in the analysis of study data in order to answer the study objectives as defined above. Populations for analysis, data handling rules, statistical methods, and formats for data presentation are provided. The statistical analyses and

summary tabulations described in this SAP will provide the basis for the results sections of the clinical study report (CSR) for this trial.

#### 2. STUDY DESIGN

# 2.1. Synopsis of Study Design

This study is a prospective, open-label, randomised, active-controlled, parallel group, multicenter, phase 3 study investigating the safety and efficacy of PA21 (Velphoro®) and calcium acetate (Phoslyra®) in paediatric and adolescent CKD subjects with hyperphosphataemia.

Approximately 130 subjects will be randomised to either PA21 (approximately 100 subjects) or to Phoslyra (approximately 30 subjects) with age as stratification factor.

Throughout the study, subjects randomised to receive PA21 will be provided with the most appropriate formulation i.e., either powder for oral suspension (for subjects <6 years) or chewable tablet (for subjects ≥6 years). For Phoslyra, only oral solution will be dispensed.

The study will consist of a maximum of 43 weeks including a screening period, a washout period, a treatment period split into 2 stages, and a follow-up period. Screening should be up to 4 weeks. The washout period should be of 1-3 weeks to allow sufficient time for washout of previous Phosphate Binders (PBs). Of note, subjects already receiving a PB but with age related serum phosphorus levels (Table H of the protocol) may be eligible for randomisation without a washout period. Treatment period will be split in 2 stages:

- Stage 1 is a dose titration period of PA21 and Phoslyra for up to 10 weeks. PA21 subjects will receive PA21 at a starting dose based on their age, as detailed in Table 3 from protocol. Phoslyra subjects will receive Phoslyra, either at a starting dose as detailed in Table 5 from protocol, or, if considered more appropriate by the Investigator, at an equivalent dose of their previous PB, calcium-based or sevelamer. Doses of PA21 or Phoslyra will be increased or decreased as required for efficacy (to achieve age specific target serum phosphorus level as indicated in Table 11 from protocol), provided a subject has been receiving that dose for a minimum of 2 weeks, and for safety or tolerability reasons at any time. Increases or decreases in dose and maximum doses are detailed in Table 4 from protocol for PA21, and Table 5 and Table 6 from protocol for Phoslyra. From Week 4, once a subject achieves the age specific target serum phosphorus level, as indicated in Table 11 from protocol, they can move to Stage 2.
- Stage 2 is a long-term safety extension of PA21 and Phoslyra for 24 weeks. All subjects will enter this safety extension and will continue on the dose they received at end of stage 1, unless a dose change is required. All subjects may have their dose titrated for efficacy to achieve age-specific target serum phosphorus levels and safety or tolerability reasons at any time during Stage 2.

All subjects, whether completing the study or withdrawn prematurely, will be followed up 14 days after their last study visit.

A Data and Safety Monitoring Board (DSMB) will review regularly the safety data to protect the safety of study participants.

# 2.2. Randomisation Methodology

Approximately 130 subjects will be randomised via interactive response technology to either receive PA21 (approximately 100 subjects) or to Phoslyra (approximately 30 subjects).

The randomisation will be stratified by age group and will also aim to randomise at least the minimum number of subjects from each age group as outlines in Table A from study protocol synopsis and as shown in Table 1 below:

Table 1 Minimum Number of Randomised Subjects by Age Group

Age	PA21	Phoslyra
0 to <1 year	4	1
$\geq 1$ year to $< 6$ years	10	3
≥6 years to <9 years	10	3
≥9 years to <18 years	10	3

# 2.3. Stopping Rules and Unblinding

The study will be conducted in an open-label manner. However, the sponsor will not receive any IxRS data or data summarised by treatment groups before the database lock in order to preserve the integrity of the trial. In particular during the DSMB meeting, the sponsor will not attend the closed session of the meeting where data splitted by treatment could be presented.

# 2.4. Study Procedures

The schedule of assessments and blood samples, as outlined in the Tables 1 and 2 from study protocol, is provided in Table 2 and Table 3 below.

Table 2 **Schedule of Assessments** 

		v	Vashout	(2)	Treatment Period											Follow-Up:	
	Screen(1,2,3)	(Visits Only for Subjects on PBs)			Stage 1  Titration Period							Stage 2 Safety Extension 					2 Weeks After Last Visit 
Week (PB washout)(2)	Up to -7	-3	-2	-1	BL	1	2	4	6	8	10	14	18	22	28	34	36
Week (PB naïve) 	Up to -4	No	t Requi	red	1												
Visit	1	2	3	4	5	6	7	8	9	10	11	12	13	14	15	16 	17 
Informed consent/assent	X																
Eligibility criteria	X				X												
Demography	X																
Medical/surgical history	X																
Physical examination	X											X				X	
Height and weight	X				X			X			X	X		X		X	
Vital signs (blood pressure, heart rate, temperature)	X				X			X			X	X		X		X	
Blood samples: details in Table 2																	
Call to IRT	X	X	X	X	X	X	X	X	X	X	X	X	X	X	X	X	X
Dispense subject identification card					X												
Dialysis parameters	X	X	X	X	X	X	X	X	X	X	X	X	X	X	X	X	
Dialysis parameters for Kt/V 	X	X	X	X	X	X	X	X	X	X	X	X	X	X	X	X	
Randomization					X												
Dispense study medication					X	X	X	X	X	X	X	X	X	X	X		
Returned study medication count						X	X	X	X	X	X	X	X	X	X	X	
Patient reported palatability and acceptability								X								X	
AE/SAE monitoring	X	X	X	X	X	X	X	X	X	X	X	X	X	X	X	X	X
Concomitant medications	X	X	X	X	X	X	X	X	X	X	X	X	X	X	X	X	X
Discuss and advise on subject's diet	X	X	X	X	X	Х	X	X	X	Х	X	X	X	Х	X	X	

 Laboratory data must be available prior to washout and randomization to check that all laboratory eligibility criteria have been met. Subjects may be rescreened once if, for example, they have a positive pregnancy test, have an active infection or if they are taking antibiotics. Subjects who need to be rescreened will be withdrawn from the study (as screen failures) and enrolled again.

 For subjects requiring a washout period, Visit 2 to be scheduled 5 to 28 days after the screening visit. Washout visits to be scheduled in relation to Visit 2: Visit 3 is 7 ±2 days, Visit 4 is 14 ±2 days, and baseline is  $21\pm2$  days. The washout period, if required, is up to 3 weeks  $\pm2$  days and cannot begin until the results from the screening visit are available for assessment of study eligibility.

 Where clinical chemistry test is conducted, serum phosphorus, serum total corrected calcium and albumin will be included therefore separate tests are not required at these visits.

 Wherever possible a sample for central laboratory analysis of these parameters should be obtained at the final visit of Stage 1.

 Exclude these blood tests in subjects <36 months but provide value if available from routine clinical assessment. Samples for bone marker assessment will be obtained and may be stored (frozen) for later

 Any visit where this value is available from routine clinical assessment.

# 2.5. Efficacy, Pharmacokinetic, and Safety Variables

## 2.5.1. Efficacy Variables

## 2.5.1.1. Primary Efficacy Endpoint

The primary efficacy endpoint is the change in serum phosphorus levels from baseline to the end of Stage 1 in PA21 group. It is based on central laboratory data; in case of missing data, the change from baseline will be computed using pre- and post-treatment values from the local laboratory (see Section 4.2.8).

## 2.5.1.2. Secondary Efficacy Endpoints

The following secondary endpoints based on central laboratory measurement are planned for analysis:

- Change in serum phosphorus levels from baseline to the end of Stage 1 in Phoslyra group
- Change in serum phosphorus levels from baseline to the end of Stage 2 in both groups

In case of missing central laboratory data, the change from baseline will be computed using preand post-treatment values from the local laboratory (see Section 4.2.8).

The following secondary endpoints based on both central and local laboratory measurements are planned for analysis:

- Serum phosphorus values at each visit during Stages 1 and 2
- Percentage of subjects with serum phosphorus level in the age related target range (Table D from the study protocol synopsis; Table 4 below) at each visit.
- Percentage of subjects with serum phosphorus level within the age related normal range (Table 5) at each visit.

Table 4 Age Related Serum Phosphorus Targets Post-Randomisation

Age	mmol/L	mg/dL
0 to <1 year	1.62-2.52	5.0-7.8
$\geq 1$ year to <6 years	1.45-2.10	4.5-6.5
≥6 years to <13 years	1.16-1.87	3.6-5.8
≥13 years to ≤18 years	0.74-1.45	2.3-4.5

Note: This table comes from National Kidney Foundation Kidney Disease Outcomes Quality Initiative Nutrition Guidelines, 2008, and was slightly modified to include 18 year in the last category.

Table 5 Age Related Normal Range of Serum Phosphorus

Age	mn	mg	g/dL	
	Lower Limit	Upper Limit	Lower Limit	Upper Limit
0 to <1 year	1.36	2.62	4.2	8.1
$\geq 1$ year to <6 years	1.03	1.97	3.2	6.1
≥6 years to <9 years	1.03	1.97	3.2	6.1
≥9 years to <10 years	1.03	1.97	3.2	6.1
≥10 years to <15 years	1.00	1.94	3.1	6.0
≥15 years to ≤18 years	0.71	1.65	2.2	5.1

Note: This table comes from Covance central laboratory normal range, and was slightly modified to include 18 year in the last category.

#### 2.5.2. Pharmacokinetic Variables

Not applicable.

## 2.5.3. Safety Variables

#### 2.5.3.1. Primary Safety Endpoint

The primary safety endpoint is the AE profile, and percentage of treatment withdrawals due to AEs (treatment withdrawals due to AEs information will be retrieved from the Treatment Termination eCRF page).

## 2.5.3.2. Secondary Safety Endpoints

The following safety secondary endpoints are planned for analysis:

- Serum total corrected calcium at each time point and change from baseline
- Percentage of subjects who develop at least 1 episode of sustained hypercalcaemia (defined as total calcium value>upper safety limit from Table 6 (Table J from the study protocol synopsis) confirmed by repeat sample 1 week later) after start of treatment
- Serum total corrected calcium-phosphorus product at each time point and change from baseline, where serum total corrected calcium-phosphorus product correspond to the product of serum total calcium and Phosphorus, expressed in mmol/L (serum total calcium and Phosphorus units must be the same).
- Serum iPTH levels at each time point and change from baseline
- Routine biochemical/haematological laboratory tests (blood iron parameters, Vitamin D parameters and bone markers)
- Vital signs

Table 6 Age Related Safety Limits of Total Calcium

Age	Upper S	afety Limit	Lower Sa	fety Limit
	mmol/L	mg/dL	mmol/L	mg/dL
0 to <1 year	2.75	11.0	<1.9	<7.6
≥1 year to <6 years	2.70	10.8	<1.9	<7.6
≥6 years to <13 years	2.60	10.3	<1.9	<7.6
≥13 years to ≤18 years	2.60	10.2	<1.9	< 7.6

Note: Upper safety limits were based on National Kidney Foundation Kidney Disease Outcomes Quality Initiative Nutrition Guidelines, 2008. Lower limit were based on literature (Paediatric Nephrology, 2nd edition) and personal communication. Both limits were slightly modified to include 18 year in the last category.

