## 4.9.1. Primary Safety Endpoint: Adverse Events

Adverse events will be coded using MedDRA and displayed in tables and listings using System Organ Class (SOC) and Preferred Term.

Analyses of adverse events will be performed for those events that are considered treatment emergent, where treatment emergent is defined as any adverse event with onset after the administration of study medication through the end of the study or any event that was present at baseline but worsened in intensity.

Adverse events are summarised by subject incidence rates, therefore, in any tabulation, a subject contributes only once to the count for a given adverse event (SOC or preferred term using the worst severity and the strongest relationship). The number of events will be reported as well in the summary tables. Multiple occurrences of the same TEAE in one subject during the same treatment in the trial will be counted as multiple events in the frequency counts for adverse events.

All TEAE summaries will be generated by treatment group and for both periods cumulatively, i.e. until end of stage 1 and until end of stage 2.

An overview of adverse events will be presented and will include the number and percentage of patients as well as the number of events with at least one:

- Treatment-emergent adverse events
- Treatment-related treatment-emergent adverse events
- Serious treatment-emergent adverse events
- Treatment-emergent adverse events leading to study drug discontinuation
- Treatment-emergent adverse events leading to Death
- Severe treatment-emergent adverse events

This table will be also repeated for any treatment-emergent adverse event of special interest (listed in Table 8 below). The overall summary of TEAEs will be also repeated by treatment group and overall maximum dose prescribed (see Table 9) during the trial. Results of the TEAE analysis by overall maximum dose prescribed may be confounded as the dose prescribed depends on the age. Therefore, a summary table with descriptive statistics for age will be provided for each overall maximum dose prescribed category by treatment.

The number and percentage of subjects as well as the number of events with the following adverse events will be presented by SOC and PT:

- with any treatment-emergent adverse event,
- with any treatment-emergent adverse events by causality assessed by the Investigator (related, unrelated),

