#### 4.9.2. Secondary Safety Endpoints

For serum total corrected calcium and serum total corrected calcium-phosphorus product expressed in mmol/L and mmol/L respectively, absolute value and change from baseline value

based on both central and local laboratory data, separately, will be described at each time point by treatment group.

For serum intact parathyroid hormone (iPTH) levels, absolute value and change from baseline value based on central laboratory data will be described at each time point by treatment group and will be expressed in both pmol/L and ng/mL units.

Percentage of subjects who develop at least 1 episode of sustained hypercalcaemia (defined as total calcium value>upper safety limit from Table 6 confirmed by repeat sample 1 week later) after start of treatment will be provided by treatment group. All the records from the local and central laboratories including scheduled and unscheduled visits will be taken into account. Patient will be considered as having an episode of sustained hypercalcaemia if two consecutive assessments separated by 6 days or more have calcium value greater than the upper limit of safety.

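### The sustained-hypercalcaemia endpoint sets no condition on pre-dose calcium, so a subject already above the Table 6 limit who stays there is counted as having developed it

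*SAP*

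**What the plan says.** Section 2.5.3.2 lists the endpoint as "Percentage of subjects who develop at least 1 episode of sustained hypercalcaemia (defined as total calcium value>upper safety limit from Table 6", with confirmation by a repeat sample a week later, after start of treatment. Section 4.9.2 makes it operational: "Patient will be considered as having an episode of sustained hypercalcaemia if two consecutive assessments separated by 6 days or more" lie above the upper limit. On the data used, it says "All the records from the local and central laboratories including scheduled and unscheduled visits will be taken into account". The result goes into Table 14.4.6, by treatment group, on the Safety Population.

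Neither section mentions the baseline value, although 4.2.1 defines baseline as the latest measurement before the first dose, and Table 3 schedules corrected calcium and albumin at the baseline visit.

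For adverse events, section 4.9.1 does deal with baseline. An event counts as treatment-emergent if its onset follows dosing, or if it is "any event that was present at baseline but worsened in intensity".

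The name of the analyte varies:
- The endpoint definition says total calcium, and the limits in Table 6 are headed "Age Related Safety Limits of Total Calcium".
- The decision rule in 4.9.2 speaks only of a calcium value: "if two consecutive assessments separated by 6 days or more have calcium value greater than the upper limit of safety".
- The neighbouring endpoint is "Serum total corrected calcium at each time point and change from baseline", and Table 3 also schedules corrected calcium.
- Section 4.9.3 and Table 10 list total and corrected calcium as separate parameters.

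**The concern.** A percentage who develop a condition should describe new cases. As written, the rule cannot tell a subject whose calcium rose on study drug from one who entered with high calcium and stayed there.

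Some carry-in is plausible. Section 2.1 shows that calcium-based binders are among the previous treatments, since a Phoslyra subject may start "at an equivalent dose of their previous PB, calcium-based or sevelamer". It also allows some subjects already on a binder to be randomised without washout.

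This is the only planned per-subject summary of calcium against the Table 6 limits. Section 1.1 gives the Phoslyra arm the role of a descriptive comparison with a calcium-based binder, so the two percentages will be read side by side. With about 30 subjects planned on Phoslyra, a few carried-in cases would be visible.

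The varying analyte is a smaller matter, but two programmers could derive different versions of Table 14.4.6 from the same text.

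**Working it through.** The SAP states no rate, sample size or power for this endpoint, so there is no figure to reproduce. The check has three parts.

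**1. Following the rule exactly.** Take a child aged 6 or over (Table 6 upper limit 2.60 mmol/L) with calcium above 2.60 at Visit 5, before dosing, and again at Visits 7 and 8. By Table 2 these last two fall at Weeks 2 and 4, two weeks apart, so the 6-day condition is met. Both values follow the first dose. The child counts as having developed sustained hypercalcaemia, although nothing changed on treatment. Under the 4.9.1 rule the same finding, reported as an adverse event, would count only if it worsened.

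**2. Possible size (all inputs assumed except the limit and the sampling schedule).**
- Limit: 2.60 mmol/L (Table 6, age 6 and over).
- Samples: one pre-dose and 10 post-dose. Table 3 gives calcium at Visits 7 to 16, ten visits, for a subject who attends all of them.
- Mean calcium 2.35, 2.40 or 2.45 mmol/L; between-child SD 0.10 or 0.12; within-child SD 0.08, 0.10 or 0.12. That makes 3 × 2 × 3 = 18 combinations.
- No drug effect and no exclusion for raised calcium at entry.
- Model: value = child's own mean + independent error. Episode = two consecutive post-dose values above 2.60. Simulated with 400,000 children per combination.

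The share of episodes that occur in children above 2.60 at baseline runs from 27% (mean 2.35, SDs 0.10 and 0.12) to 52% (mean 2.45, SDs 0.12 and 0.08).

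Middle case (mean 2.40, between-child SD 0.12, within-child SD 0.08):
- Above the limit at baseline: 1 − Φ(0.20 / √(0.12² + 0.08²)) = 1 − Φ(1.387) = 8.3%.
- Episode given high baseline: 62%. Episode given baseline not high: 6.3%.
- Counted overall: 0.083 × 0.62 + 0.917 × 0.063 = 0.051 + 0.058 = 10.9%.
- Share already high: 0.051 / 0.109 = 47%.

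**3. Effect on the contrast.** Let c be the share of subjects who are high before dosing and persist, and r the new-onset rate. Then counted rate = c + (1 − c) × r. Assume, for illustration only, r = 2% on PA21 and 15% on Phoslyra.

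| c | PA21 | Phoslyra | Difference (points) | Ratio |
|---|---|---|---|---|
| 0% | 2.0% | 15.0% | 13.0 | 7.5 |
| 5% | 6.9% | 19.25% | 12.35 | 2.8 |
| 10% | 11.8% | 23.5% | 11.7 | 2.0 |

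At c = 5%, 0.05 / 0.069 = 72% of the PA21 cases would be pre-existing. The difference between arms moves little and the ratio moves a lot. With c = 0 nothing changes.

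**Analyte.** The SAP gives no correction formula. Assume corrected − total = s × (40 − albumin in g/L), with s between 0.015 and 0.025 mmol/L per g/L. At albumin 30 g/L the gap is 10s = +0.15 to +0.25 mmol/L; at 45 g/L it is −5s = −0.075 to −0.125. The choice of analyte can therefore decide whether a value exceeds 2.60, in either direction.

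**The case against.** The strongest reply is that the effect may be small.

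- **Eligibility.** The notes to Table 2 require laboratory eligibility data before washout and randomisation, and those criteria, which are not shown, may exclude raised calcium. This stands as a reason not to claim a size. It would not close the gap fully: screening can precede baseline by up to 4 weeks, or up to 7 with washout.
- **Washout.** One to three weeks is foreseen for previous binders, and entry without washout is an exception of unstated frequency. This also stands.
- **Descriptive use.** Only the primary endpoint is formally tested, randomisation makes carry-in similar in expectation in both arms, and the risk difference barely moves. The large shift is in the ratio, which the SAP does not plan. This limits the consequence, but each arm's percentage is still mislabelled.
- **Other outputs.** Change-from-baseline tables, shift tables and listings let a reader trace pre-existing cases, and calcium metabolism disorders are an event of special interest under the treatment-emergent rule. None of these corrects the percentage in Table 14.4.6.
- **Limits of the fix.** In the middle case about 53% of the no-drug-effect episodes occur in children not high at baseline, so a baseline split removes only part of the background.

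Two stronger readings are tempting. A reader might infer that a high pre-dose value may serve as the first of the confirming pair, because all records are used. That is strained: both sections place the episode after start of treatment, and the sentence on records concerns laboratory source and visit type. A reader might also infer that the endpoint definitely uses uncorrected calcium and so misses children with low albumin. The SAP does not settle this. It defines the corrected calcium-phosphorus product itself in terms of serum total calcium, and the rule in 4.9.2 names no analyte.

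**Conclusion.** The point holds. The endpoint is worded as new onset, but its rule also counts persistence of a pre-dose state. It inflates the percentage in both arms and somewhat dilutes the descriptive contrast. It does not touch the primary analysis or any test.

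The true size cannot be found from the SAP. The range of 27% to 52% of counted episodes, and the middle case of 10.9% against 6.3%, rest on assumed calcium distributions, no drug effect and no calcium screening at entry. If eligibility excludes most raised values, the effect is smaller; if nobody enters above the limit, it is nil.

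On the analyte, the supported finding is inconsistency. Low-albumin cases are missed only if uncorrected calcium turns out to be the one used, and above the albumin reference the error reverses.

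**What to change.** In 2.5.3.2 and 4.9.2:
1. State that both values of the confirming pair are taken after the first dose.
2. Report the percentage who develop an episode among subjects whose last pre-dose value is at or below their Table 6 upper limit.
3. In Table 14.4.6, show subjects already above the limit at baseline in a separate block, with the number whose high calcium persisted.
4. Reconcile the calcium wording across the endpoint definition, the Table 6 title, the 4.9.2 rule, the neighbouring endpoint and Table 3. Name one analyte that matches what the Table 6 limits were set for, state the correction formula if one applies, and report the other analyte as supportive.

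The cost is SAP wording, one baseline flag and one extra table block. The denominator becomes slightly smaller. No new data are needed, since baseline calcium and albumin are already scheduled.
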